We are proposing a prospective, randomized, two-arm, open label pilot study to demonstrate the in vivo effects previously seen in preclinical studies using cervical cancer cell lines16-20. Study participants will be recruited from the Grady Cancer Center of Excellence and the Infectious Disease Program at Grady's Ponce Clinic. A convenience sample of 40 HIV uninfected and infected participants with biopsy-proven HSIL will be randomized to one of two arms (2000 mg of curcumin powder in capsules or placebo inserted intravaginally weekly at bedtime for 12 weeks, (excluding the time when they are on their menses) as demonstrated in the schema.

Cervical cytology, vaginal swabs, colposcopies and biopsies will be performed every 4 weeks during each study visit for the study duration for the primary objectives outlined in specific aims 1-3. These time points were selected to acquire cervical samples prior to treatment, during treatment and 4 weeks after treatment completion (LEEP specimen). Study drug and placebo will be administered during weeks 1-12 (12 weeks of treatment) and no treatment will be administered during weeks 13-16 (washout period). Cervical biopsies will be performed in areas with a colposcopic suggestion of HSIL disease and four additional cervical punch biopsies (one specimen from each of four quadrants) of the cervix will be done for downstream biomarker analysis. The laboratory, pathology and data analysis staff will be blinded to treatment arm. The clinicians performing the colposcopies nor the participants will not be blinded secondary to the evident color of curcumin.

Study Population

HIV uninfected and infected women will be recruited for this study. We will focus only on HIV infected women without an AIDS defining disease, given that the risk of progression from high grade lesions to invasive carcinoma is faster in HIV infected subjects who are significantly immune compromised.

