Acceptability Questionnaires: Descriptive statistics on subject and partner responses from the acceptability questionnaires will be reported.

Power and sample size calculation: The expression of E6/7 is the primary endpoint of the study and will be used in the power and sample size calculation with a two sample two sided t-test. In this study, we will enroll 20 patients in each of the two groups. Therefore, the group sample sizes of 20 in Curcumin group and 20 in placebo group will achieve at least 80% power at the significant level of 0.05 to detect a difference of a ratio of 1.536 or higher in the expression of E6/ between the two groups, assuming the coefficent of variation is 0.5.

SAFETY EVALUATION:

Adverse Events (AEs) and Serious Adverse Events (SAEs)

This investigational agent is studied under IND # 103496 and monitoring will be performed per previously agreed upon FDA guidance.

There may be some minor irritation from the intravaginal curcumin to the vaginal mucosa and staining of underwear. Other side effects which can happen include the upset stomach, diarrhea, burning sensation in the vagina, dizziness, insomnia, rash, pruritus generalized, and fever. The literature shows that over 13 subjects in United States and 151 subjects in India (10) have been studied with curcumin without any serious adverse effects.

Our phase I study has shown that curcumin is safe in dosage up to 2000mg.

Any patient intervention related adverse effects, an unanticipated problem, or reportable protocol deviation/ non-compliance will be reported to the Emory IRB office according to IRB P & P and to the FDA according to regulations.

Any serious adverse effects will be communicated by the principal investigator to the Emory IRB using the standard adverse event reporting forms.

SAEs will be defined per FDA standards and include those that result in death, are life threatening, result in a disability, cause for hospitalization, or to a congenital abnormality or birth effect. SAEs will be reported to the DSMC, IRB and FDA and manufacturer as required.

CLINCAL OUTCOMES AND MEASURES:

The table below gives the descriptions to be used to document findings during colposcopy.

| Colposcopic findings | | | | Presence | |
|----------------------|----------------------|----------------------|----------------------|----------|--------|
| | Grade 1 | Grade 2 | Grade 3 | | |
| | (Mild) | (Moderate) | (Severe) | Present | Absent |

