| | Definitions provided | Definitions provided | Definitions provided | | |
| Peeling | If both the | If either the | If they involve | | |
| Ulcer | epithelium | epithelium | disruption of | | |
| Abrasion | and the blood | is | the | | |
| Ecchymosis | vessels are | superficially | epithelium; | | |
| Petechiae | intact | disrupted or | an area of the | | |
| Erythema | | the blood | epithelium | | |
| Edema | | vessels are | with bleeding | | |
| Grossly white | | disrupted | should be | | |
| lesion | | | considered | | |
| Sloughing | | | deeply disrupted | | |
| Laceration | | | | | |

Colposcopic findings (present or absent) will be summarized at each visit. Findings will be counted once, attribute to the time point/visit at which they were first detected, and described on the basis of their characteristics when they were first detected. The same criteria outlined in the WHO Update Colposcopy Manual to assess toxicity and mucosal damage to the cervix, vagina and perineum will be carefully followed.

DATA AND SAFETY MONITORING PLAN (DSMP):

The primary risk to this study relates to potential complications with vaginal sampling, vaginal mucosa irritation and colposcopy with targeted cervical biopsies/LEEP. [name] will monitor subject safety and respond to occurrences if AEs/SAEs in a timely manner.

The Data and Safety Monitoring Committee (DSMC) of the Winship Cancer Institute will provide oversight for the conduct of this study. The DSMC functions independently within Winship Cancer Institute to conduct internal monitoring functions to ensure that research being conducted by Winship Cancer Institute Investigators produces high quality scientific data in a manner consistent with good clinical practice (GCP) and appropriate regulations that govern clinical research. Depending on the risk level of the protocol, the DSMC review may occur every 6 months or annually.

For this study: deemed Moderate Risk, initial study monitoring will occur within 1 year from the date of the first subject accrued, with 2 of the first 5 subjects being reviewed. Subsequent monitoring will occur in routine intervals per the Winship Data and Safety Monitoring Plan (DSMP).

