| Colposcopic findings | Grade II or greater Grade I not resolved in 2 weeks | • N/A | One participant report the product-related symptoms at a specified grade | Prompt notification of DSMB, IRB, NIH, FDA and CTRC. All product application is help until further notice, follow up and resolution |

This study does involve intervention with a product and the protocol does require the collection of sensitive and confidential information, biological samples (genital tract), physical examination, colposcopy and pharmacological intervention (curcumin). As with any study that includes these procedures there may be side effects from the study procedures that are not known at this time. However, for those common risks and discomforts expected in this study they are outlined in the consent forms, and also listed below with the methods to minimize any associated risk:

1: Physical exams

Participants may feel some minor physical discomfort. This should be minor and will go away quickly. All physical tests and examinations will be performed by a trained and experienced health care practitioner.

2: Biologic Sample collection (genital tract sample collection) and colposcopy with biopsy:

For genital tract sample collections, participants may feel some minor physical discomforts and experience spotting or bleeding from cervical biopsy collections.

- 3: As this study involves pharmacological intervention subjects will be administered a pregnancy test will be administered by an experienced health care practitioner before enrollment and at each study visit during the course of the study.
- 4. This study requires intravaginal placement the capsules (curcumin or placebo). Pill diaries will be given and monitored at each visit. Subjects will also be contacted twice a week to ensure adherence and be given the ability to report any adverse events/side effects like vaginal discharge and vulvo-vaginal irritation.
- 5. Subjects will be informed of potential risks and sign a written informed consent for participation. Subjects will be asked to agree to the use of reliable birth control: Combined oral contraceptive pill (OCP), Long Lasting Reversible Contraceptive (LARCP), Bi-Lateral Tubal Ligation (BLT) and Depo-Provera Shot/Birth control shot.
- 5b. Partner notification letters will indicate the need for condom use and the risk of discoloring and/or irritation if a condom is not used when having vaginal sex with an enrolled female participant.

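### The colposcopy summary fixes each finding's description at first detection, so a later rise in grade is reported at the earlier, lower grade, and no worst-grade or shift summary is stated.

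*Combined protocol and SAP*

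**What the plan says.** The Clinical Outcomes and Measures section introduces a grading table with these words: "The table below gives the descriptions to be used to document findings during colposcopy". The table lists ten named findings (peeling, ulcer, abrasion, ecchymosis, petechiae, erythema, edema, grossly white lesion, sloughing, laceration). It defines Grades 1 (mild), 2 (moderate) and 3 (severe) by whether epithelium and blood vessels are intact, and it has present/absent columns.

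Two reporting rules follow:

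- By visit: "Colposcopic findings (present or absent) will be summarized at each visit".
- Across visits: "Findings will be counted once, attribute to the time point/visit at which they were first detected", and findings are "described on the basis of their characteristics when they were first detected".

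The section also invokes "The same criteria outlined in the WHO Update Colposcopy Manual to assess toxicity and mucosal damage" for how the tissues are assessed.

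Four other places bear on the point:

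- The Data and Safety Monitoring Plan includes among the study's primary risks "vaginal mucosa irritation and colposcopy with targeted cervical biopsies/LEEP". It also sends aggregate safety data, of unspecified content, to the final monitoring committee review.
- The Stopping/Pausing Rules table lists colposcopic findings under its symptom-or-adverse-event column. It acts at Grade II or above, or at Grade I unresolved after 2 weeks, on the criterion "One participant report the product-related symptoms at a specified grade".
- Item 8 of the risk-minimisation list after that table provides for regular investigator review of summaries of Grade 3 or 4 adverse events and of other targeted events, which are not defined.
- Research Design and Methods states: "The clinicians performing the colposcopies nor the participants will not be blinded secondary to the evident color of curcumin".

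**The concern.** Counting a finding once, as first seen, describes onset. It cannot describe worsening. The present/absent summary cannot do so either, because a finding that goes from Grade 1 to Grade 2 is present both times.

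This matters most for findings already there before treatment. All participants have a high-grade cervical lesion and are examined before the first dose, so some are likely to enter with erythema or a white lesion. If such a finding worsens on product, the stated rule places it at baseline at its baseline grade, and it then looks like a pre-existing mild finding. From week 4 onward, biopsy sites can in the same way supply an earlier, milder entry that a later rise is folded into.

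At stake is the severity description for a risk that the plan itself names as primary, in a pilot meant to inform a larger trial. The efficacy comparison is not at stake.

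**Working it through.** The plan states no figure on this point, so there is none to reproduce. The check sets the stated outputs side by side and traces a finding through them.

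**Inputs.** Three grades and the two reporting rules (Clinical Outcomes and Measures); colposcopy at screening, baseline and weeks 4, 8, 12 and 16 (Schedule of Events); no treatment in weeks 13 to 16 (Research Design and Methods); the pausing rule; the adverse event summaries in item 8. The reading that grade is one of the fixed characteristics is an inference. It is the natural one, since the grades are the descriptions that the table supplies.

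**Trace for one named finding in one woman:**

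| Course | By-visit summary | First-detected summary | Pausing rule | Item 8 summaries |
|---|---|---|---|---|
| Grade 1 at baseline, Grade 2 at week 8 | Present | One finding, baseline, Grade 1 | Grade threshold met at week 8; acts if judged product-related | Outside the Grade 3-4 summary; shown only if classed as targeted |
| Grade 1 at week 4, Grade 3 at week 12 | Present | One finding, week 4, Grade 1 | Grade threshold met by week 12 at the latest; acts if judged product-related | Shown if recorded as an adverse event |
| Absent at baseline, Grade 2 at week 8 | Present from week 8 | One finding, week 8, Grade 2 | Grade threshold met; acts if judged product-related | Outside the Grade 3-4 summary; shown only if classed as targeted |

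The by-visit column takes that summary as prevalence, which the text does not settle. The third row shows that the rule works for a finding that appears once at its final grade. The first two rows show the gap. With three grades, the possible rises are 1 to 2, 1 to 3 and 2 to 3, and the first-detected summary shows none of them as a rise.

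**Is a rise tabulated elsewhere?** No worst-grade, maximum-grade or shift summary of colposcopic findings is stated. The item 8 summaries and the aggregate safety data might contain a rise, but the documents do not say whether a worsened colposcopic finding is recorded as an adverse event or counts as targeted.

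**Size.** The documents give no rate of findings or of worsening, so the understatement cannot be calculated. The precision of a corrected table can be shown for assumed counts among 20 women in an arm. The exact 95% limits are the 2.5% point of Beta(k, 21 − k) and the 97.5% point of Beta(k + 1, 20 − k). For k = 0 the upper limit is 1 − 0.025^(1/20) = 16.8%.

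| Women with a rise (assumed) | Proportion | Exact 95% interval |
|---|---|---|
| 0 of 20 | 0% | 0 to 16.8% |
| 1 of 20 | 5% | 0.1 to 24.9% |
| 2 of 20 | 10% | 1.2 to 31.7% |
| 4 of 20 | 20% | 5.7 to 43.7% |

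These counts illustrate precision and are not evidence of a problem. The widths show that the table can only be descriptive.

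**Background from biopsies.** Assume four quadrant biopsies at each of baseline and weeks 4, 8 and 12. A woman in either arm then reaches the week 12 colposcopy after 3 × 4 = 12 of them and the week 16 colposcopy after 4 × 4 = 16, plus targeted biopsies. Some new or worse findings may therefore come from the procedures.

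**The case against.** A reader might infer that a later rise in grade appears nowhere in the planned reporting, or that it would go unnoticed. The documents support neither reading.

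- **Adverse event summaries.** The pausing table places colposcopic findings under its symptom-or-adverse-event column, and summaries of Grade 3 or 4 and targeted events are planned. A rise to Grade 3 could appear there if it is recorded as an adverse event, and a rise to Grade 2 if it is classed as targeted. This stands: the gap is that the link is unspecified, not that it is shown to be absent.
- **Pausing rule.** It is not tied to first detection. Every rise ends at Grade 2 or 3, so every rise meets its grade threshold. One participant is enough to prompt notification and a hold on product, so product-related rises should not build up unseen. This also stands. But the rule is a trigger, not a tabulation, and it needs a judgement of relatedness in a trial where the colposcopists know the arm. Worsening judged unrelated to product is left to the summaries.
- **What counts as the same finding.** The plan does not say whether the unit is the lesion or the named type. The WHO manual was not available for this review. Worsening may also be recorded under another name: erythema that reaches Grade 2 involves disrupted epithelium or vessels and might be entered as abrasion or petechiae, with its own visit and grade. For an ulcer or laceration, Grade 1 (intact epithelium and vessels) is hard to satisfy at all. These points narrow how often the rule would mislead, but they do not remove the cases where the same name is kept.
- **Importance.** Safety is not one of the three specific aims, and the table would rest on unblinded grading with repeated biopsies as background. That is a fair reason to treat the point as minor.

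**Conclusion.** The point holds in a limited form. As written, the colposcopy summary reports a finding that rises in grade at its earlier, lower grade, and as a pre-treatment finding if first seen at baseline. No worst-grade or shift summary of colposcopic findings is stated, and whether a rise reaches the adverse event summaries or the aggregate safety data is left open.

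This rests on two assumptions: that grade is one of the characteristics fixed at first detection, and that a worsened finding under the same name is the same finding.

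It would go too far to say that safety information is lost or that an undercount of known size exists. The grading table implies that grades are recorded at colposcopy, so a better summary can be produced from them. The primary E6/E7 analysis does not depend on this rule. It is a cheap improvement to a descriptive safety summary.

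**What to change.** Add one sentence to Clinical Outcomes and Measures and one descriptive table by arm, built from the grades already recorded. For each named finding the table should show:

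1. the worst post-baseline grade per woman, with weeks 4, 8 and 12 shown separately from the week 16 washout visit;
2. at each visit, the number of women whose finding is new or of higher grade than at baseline.

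Keep the first-detected table as supplementary. State whether worsened colposcopic findings are recorded as adverse events, and whether the by-visit present/absent summary is a prevalence and is given by arm. The lack of any stated split by arm is a separate omission that the same sentence can settle.

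Add a note that the table is descriptive, rests on unblinded grading, and must be read against placebo because repeated biopsies in both arms can cause findings.

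The cost is one extra table with limited precision. Examinations, biopsies and the pausing rule stay as they are.
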